8.2. Serious Adverse Event Procedures

Reference Safety Information

The reference for safety information for this study is the Investigator's Brochure which the Sponsor has provided under separate cover to all Investigators.

Reporting Procedures

All initial and follow-up SAE reports must be reported by the Investigator to the Pharmacovigilance vendor (see Table 1) within 24 hours of the first awareness of the event. Note: The 24 hours reporting requirement for SAEs does not apply to reports of abuse, misuse, or overdose (see Section 8.1.7) unless they result in an SAE.

The Investigator must complete, sign, and date the Serious Adverse Event Form and verify the accuracy of the information recorded on the form with the corresponding source documents and fax or e-mail the form to the Pharmacovigilance vendor.

Serious Adverse Event Definition

A *Serious Adverse Event* (SAE) is any untoward medical occurrence (whether considered to be related to investigational product or not) that at any dose:

- Results in death
- Is life-threatening

NOTE: The term 'life-threatening' in the definition of 'serious' refers to an event in which the subject was at risk of death at the time of the event; it does not refer to an event which hypothetically might have caused death if it was more severe.

- Requires inpatient hospitalization or prolongation of existing hospitalization
- Results in persistent or significant disability/incapacity
- Is a congenital abnormality/birth defect

• Is an important medical event. Note: Important medical events that may not result in death, be life-threatening, or require hospitalization may be considered an SAE when, based upon appropriate medical judgment, they may jeopardize the subject and may require medical or surgical intervention to prevent 1 of the outcomes listed in this definition. Examples of such medical events include allergic bronchospasm requiring intensive treatment in an emergency room or at home; blood dyscrasias or convulsions that do not result in inpatient hospitalization; or the development of drug dependency or drug abuse.

Hospitalizations, which are the result of elective or previously scheduled surgery for pre-existing conditions, which have not worsened after initiation of treatment, should not be classified as SAEs. For example, an admission for a previously scheduled ventral hernia repair would not be classified as an SAE.

However, complication(s) resulting from a hospitalization for an elective or previously scheduled surgery that meets serious criteria must be reported as SAE(s).

8.3. Serious Adverse Event Collection Timeframe

All SAEs (regardless of relationship to study) are collected from the time the subject signs informed consent until the defined follow-up period stated in Table 2, and must be reported to the Pharmacovigilance vendor (see Table 1) within 24 hours of the first awareness of the event.

In addition, any SAE(s) considered "related" to the investigational product and discovered by the Investigator at any interval after the study has completed must be reported to the Pharmacovigilance vendor (see Table 1) within 24 hours of the first awareness of the event.

Serious Adverse Event Onset and Resolution Dates

The onset date of the SAE is defined as the date the event meets serious criteria. The resolution date is the date the event no longer meets serious criteria, the date the symptoms resolve, or the event is considered chronic. In the case of hospitalizations, the hospital admission and discharge dates are considered the SAE onset and resolution dates, respectively.

In addition, any signs or symptoms experienced by the subject prior to study entry or leading up to the onset date of the SAE or following the resolution date of the SAE, must be recorded as an AE, if appropriate.

Fatal Outcome

Any SAE that results in the subject's death (ie, the SAE was noted as the primary cause of death) must have fatal checked as an outcome with the date of death recorded as the resolution date. For all other events ongoing at time of death that did not contribute to the subject's death, the outcome should be considered not resolved, without a resolution date recorded.

For any SAE that results in the subject's death or any ongoing events at the time of death, the action taken with the investigational product should be recorded as "dose not changed" or "not applicable" (if the subject never received investigational product).

Regulatory Agency, Institutional Review Board, Independent Ethics Committee, and Site Reporting

Kadmon Regulatory Affairs (or designee) is responsible for notifying the relevant regulatory authorities of related, unexpected SAEs.

In addition, the Sponsor is responsible for notifying active sites of all related, unexpected SAEs occurring during all interventional studies across the tesevatinib program.

The Investigator is responsible for notifying the local IRB and the Sponsor of all SAEs that occur at his or her site as required.

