If subjects experience an acute onset of new and/or progressive, unexplained pulmonary symptoms such as dyspnea, cough, and fever, study drug should be held while subjects are evaluated. If interstitial lung disease is diagnosed, study drug should be discontinued and treatment administered as necessary.

Hepatotoxicity

Rare cases of hepatic failure have been reported. Confounding factors have included pre-existing liver disease or concomitant hepatotoxic medications. Liver function test abnormalities (including elevated ALT, AST, and bilirubin) have been observed in clinical studies with tesevatinib. Interruption of study drug should be considered in subjects developing liver function abnormality $> 3 \times ULN$.

Management guidelines for liver function abnormalities are provided in Table 5.

Table 5: Management Guidelines for Liver Function Abnormalities

Liver Function Abnormality	Occurrence	Action
Hyperbilirubinemia		
$2.5 - < 3 \times ULN$	1 st	Hold dose; resume dosing when recovered or reduced to mild intensity.
	2 nd	Off study.
> 3 × ULN	1 st	Off study.
AST/ALT elevations		
2.5 – < 3 × ULN	1 st	Hold dose; resume dosing when recovered or reduced to mild intensity.
	2 nd	Hold dose and discuss management with Medical Monitor.
> 3 × ULN	1 st	Hold dose and discuss management with Medical Monitor.
	2 nd	Off study.

Abbreviations: ALT, alanine aminotransferase; AST, aspartate aminotransferase; ULN, upper limit of normal

Pericardial Effusion

Pericardial effusions have been seen in oncology studies with tesevatinib. In addition, 1 subject with ADPKD receiving 50 mg tesevatinib daily developed a trace pericardial effusion. The guidelines outlined below should be followed in the event that a subject develops a pericardial effusion while receiving tesevatinib.

For an asymptomatic pericardial effusion that is at least moderate in size, a follow-up echocardiogram should be performed within 1–3 months to monitor for progression. Results of the additional echocardiogram should be discussed with the Medical Monitor to determine subject management.

Subjects should be monitored for signs and symptoms of cardiac tamponade. In addition to the monthly to bimonthly physical exam of blood pressure, pulse, respiration, weight, heart, and lung, physical exam should also asses for tachycardia, dyspnea, neck vein distension, and edema.

Adrenal Insufficiency

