9.11. Safety Analyses

Safety analyses will be based on the mITT Population.

Treatment-emergent adverse events (TEAE) will be coded using the Medical Dictionary for Regulatory Activities (Version 19.0 or higher). The number of events, incidence, and percentage of TEAEs will be presented by system organ class and by preferred term for each treatment group. Treatment-emergent adverse events will be further summarized by severity and relationship to investigational product. Adverse events related to investigational product, AEs leading to withdrawal, SAEs, and deaths will be summarized/listed.

Clinical laboratory tests (including serum creatinine, cystatin C, and eGFR), vital signs, and ECG findings will be summarized by treatment group and visit. Potentially clinically important findings will also be summarized or listed.

Physical examination, echocardiogram and ocular evaluation findings will be provided in listings.

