3.13.1 Adverse Events

AEs will be coded using the MedDRA dictionary (Version 20.0). Treatment-emergent AEs (TEAEs) are any AE occurring or worsening in severity after the first administration of study medication. All AEs (including SAEs) will be graded using the 5-point Common Terminology Criteria for Adverse Events (CTCAE) V5.0 scale (mild, moderate, severe, life-threatening, or death). Causality with tesevatinib will be classified as: definitely related; probably related; possibly related; unlikely related; or not related. Definitely related, probably related and possibly related will be combined to related, unlikely related and not related will be combined to unrelated in some safety analyses.

The number and percentage of patients who experienced at least one TEAE as well as the number and percentage of patients who experienced AEs of each specific system organ class (SOC) and preferred term (PT) will be presented. For the presentation of AE incidences, the SOCs and the PTs within each SOC will be presented by decreasing total frequency. Tabulation by maximum severity and relationship to tesevatinib will also be included by treatment group.

The TEAEs, Grade \geq 3 TEAEs, SAEs, and TEAEs leading to dose modification/discontinuation will be summarized by treatment arm, SOC, and PT. These analyses will be repeated for events considered related (definitely related/probably related/possibly related) to tesevatinib.

Subject listings will be provided for SAEs, AEs resulting in study drug discontinuation, and deaths.

Adverse events will also be presented in listings. Time to onset and duration of AEs will be included in listings, along with action taken and outcome.

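### The fatal-outcome rule can misrecord the action taken with study drug when drug was held or stopped before death (minor)

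*Protocol*

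**What the plan says.** Protocol 8.3, under Fatal Outcome, sets a recording rule whose scope is wide. For any fatal SAE "or any ongoing events at the time of death, the action taken with the investigational product should be recorded as" *dose not changed*. The only alternative is *not applicable*, reserved for subjects who never received study drug. There is no exception for drug that had already been held or withdrawn.

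Elsewhere the protocol foresees such holds and stops. Protocol 6.7 (Pulmonary Toxicity) says: "If interstitial lung disease is diagnosed, study drug should be discontinued and treatment administered as necessary". The same section provides for drug to be held or the subject taken off study for liver abnormalities (Table 5), and for drug to be held for QTcF prolongation. Protocol 4.3 names symptomatic pericardial effusion and cardiac tamponade among the adverse events that are reasons for discontinuation. It also requires the eCRF to give *Adverse event* as the reason whenever an AE is one.

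SAP 3.13.1 plans that "TEAEs leading to dose modification/discontinuation will be summarized by treatment arm, SOC, and PT". On listings it says "Subject listings will be provided for SAEs, AEs resulting in study drug discontinuation, and deaths" and "Time to onset and duration of AEs will be included in listings, along with action taken and outcome". Protocol 9.11 adds: "Adverse events related to investigational product, AEs leading to withdrawal, SAEs, and deaths will be summarized/listed".

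**The concern.** The rule instructs a site to enter something untrue whenever drug was held or withdrawn for an event that then proved fatal or was still present at death. It also reaches non-fatal, unrelated events. A rash for which drug had been stopped, still ongoing when the subject died of something else, would have to read *dose not changed*.

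These are the cases that a safety assessor reads one by one, and action taken is the field that says how the event affected dosing. The entry would also sit uneasily with two other instructions. Protocol 8.2 has the investigator verify the SAE form against source documents, and Protocol 9.1 has the monitor compare the eCRF with source. If the source says drug was stopped, the site cannot satisfy both those checks and the fatal-outcome rule.

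**Working it through.** The protocol and SAP give no figure to reproduce on this point, so the check sets the passages against each other.

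**Step 1: when is the prescribed entry true?** Take a dosed subject who dies within the collection period. Under Protocol 8.3 and Table 2 this runs from consent to the end-of-study visit, 30 days after the last dose.

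- Nothing was changed for the event before death: *dose not changed* is correct.
- Drug was held for the event, which was fatal or ongoing at death: the entry is false.
- Drug was withdrawn for the event, which was fatal or ongoing at death: the entry is false. It also contradicts the *Adverse event* reason that Protocol 4.3 requires.
- The event began after drug had already been stopped for another reason: there was no dosing left to change, but *not applicable* is unavailable because the subject had received drug.
- The event resolved before death: the rule does not apply, and the true action stands.

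**Step 2: which outputs carry the error?** Take the second and third cases above.

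- AE listings (SAP 3.13.1): action taken is displayed, so the listing is wrong whatever else is decided.
- Table of TEAEs leading to dose modification or discontinuation, its repeat for related events, and the listing of AEs resulting in discontinuation (SAP 3.13.1): no source variable is named. If action taken is the source, the event is missing. If the eCRF discontinuation reason is the source, a discontinuation can be recovered, but a temporary hold cannot.
- AEs leading to withdrawal (Protocol 9.11): again no source variable is named, so the same two possibilities apply.
- Disposition (SAP 3.4): built from the primary reason for discontinuation, so not affected.
- Exposure (SAP 3.8): built from the date of last dose, with dose interruptions listed by subject, so not affected. It shows that dosing changed but does not tie the change to an AE.
- SAE and death listings: a fatal SAE is still present in both.

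**Step 3: how many subjects?** Three things must coincide: a death in the collection period, a hold or stop for an event before that death, and that event being fatal or still ongoing. The documents give no rate for any of them, so no expected number can be calculated.

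**The case against.** The strongest reply is that the rule has a sensible purpose: to stop sites entering *drug withdrawn* merely because the subject died. That purpose is plausible, though the protocol does not state it. The wording goes further and overrides actions taken before death. The purpose survives the proposed change.

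A second reply is that the mismatch would come to light. Disposition would say *Adverse event*, exposure would show the last dose date or the interruption, and Protocol 9.1 and 9.2 provide source review and data validation. This makes silent loss less likely. It does not tell the site which entry to make, since the rule itself prescribes the false one.

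A reader might infer that these events necessarily drop out of the discontinuation tables. The documents do not support that. Action taken is the only per-event field on drug action that they name, which makes it the likely source, but the SAP mentions it only as an item in the AE listings. The table shells are in a separate document (SAP section 4). The disposition table would still count the subject.

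A reader might also put the distortion at 2 percentage points per affected subject, from 1/50 in a planned arm of 50. That arithmetic applies to the TEAE table only if the table is built from action taken, a qualifying death occurs, and no other event already places the subject in the table. It does not apply to the disposition-based rate.

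**Conclusion.** The point holds as a minor defect. The fatal-outcome rule is unconditional for dosed subjects and prescribes a wrong entry in situations that the protocol itself foresees. The certain consequence, when such a case occurs, is a wrong action taken in the AE listings. For a withdrawal there is also a conflict with the Protocol 4.3 reason. Absence from the SAP 3.13.1 dose modification/discontinuation outputs is conditional on a derivation that the SAP does not state.

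The number of subjects affected cannot be computed and may be zero. The primary endpoint, Type I error, power and analysis populations are untouched. A reader might conclude that the most serious courses are hidden from safety reporting. They are not: fatal SAEs remain in the SAE and death listings and in the SAE table, and only the recorded drug action is wrong.

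**What to change.** Replace the sentence in Protocol 8.3 (Fatal Outcome) so that action taken records what was actually done with study drug for that event before death. Keep *dose not changed* where nothing was changed before death. Use *not applicable* where the subject never received drug, or had already stopped it for another reason before the event began. Carry the same wording into any eCRF completion guidance.

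In SAP 3.13.1, name the variable that defines TEAEs leading to dose modification/discontinuation and AEs resulting in study drug discontinuation.

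The cost is one sentence in each document. No dosing or stopping rule changes.

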9. DATA MANAGEMENT AND STATISTICAL METHODS

9.1. Data Collection

The Investigators' authorized site personnel must enter the information required by the protocol on the eCRF. A Study Monitor will visit each site in accordance with the monitoring plan and review the eCRF data against the source data for completeness and accuracy. Discrepancies between source data and data entered on the eCRF will be addressed by qualified site personnel. When a data discrepancy warrants correction, the correction will be made by authorized site personnel. Data collection procedures will be discussed with the site at the site initiation visit and/or at the Investigator's Meeting. It is expected that site personnel will complete the eCRF entry within 5 business days of the subject's visit.

9.2. Clinical Data Management

Data are to be entered into a clinical database as specified in the data management plan. Quality control and data validation procedures are applied to ensure the validity and accuracy of the clinical database.

9.3. Statistical Analysis Process

Details regarding the statistical methods and definitions will be provided in the Statistical Analysis Plan. The SAP will be finalized prior to unblinding to preserve the integrity of the statistical analysis and study conclusions.

Categorical data will be summarized by frequency distributions (number and percentages of subjects) and continuous data will be summarized by descriptive statistics (mean, standard deviation, median, minimum, and maximum).

All data will be provided in by-subject listings.

All statistical analyses will be performed after the database is locked and unblinded. Statistical analyses will be performed using Version 9.1 or higher of SAS[®].

9.4. Planned Interim Analysis, Adaptive Design, and Data Monitoring Committee

There is no planned interim analysis, adaptive design, or Data Monitoring Committee in this study.

9.5. Selection of Subjects to be Included in the Analyses

The following populations will be used in this study:

• The Modified Intent-To-Treat (mITT) population: as all randomized subjects who received at least 1 dose of study drug.

• The Efficacy Population: all subjects in the mITT population who complete at least 12 months of tesevatinib or placebo treatment and have a centrally read MRI at baseline and after 12 months of treatment.

9.6. Subject Disposition

Subjects in each analysis set, as well as subjects who complete the study, and subjects who prematurely discontinue from the study will be summarized by treatment group using descriptive statistics. In addition, for subjects who prematurely discontinue from the study, the reasons for discontinuation will be summarized by treatment group.

9.7. Demographic and Baseline Characteristics

Descriptive summaries of demographic and baseline characteristics will be presented by treatment group and overall for the mITT population.

Demographics and baseline characteristics will be examined to assess the comparability of the treatment groups at baseline. Continuous variables such as subject age, weight and height will be summarized using number of observations, mean, standard deviation, median, minimum, and maximum values. Categorical variables such as subject sex and race will be summarized using number of observations and percentages for each category.

Medical history will be summarized by treatment group using the number of observations and percentages of subjects reporting each category.

9.8. Investigational Product Exposure

Summary statistics for the duration of exposure to investigational product will be presented by treatment group. In addition, the number of dose interruptions will be provided in by-subject listings.

9.9. Prior and Concomitant Medication

Prior and concomitant medications will be coded using the World Health Organization drug dictionary. Prior and concomitant medications will be listed and summarized by preferred drug name and treatment group.

9.10. Efficacy Analyses

All efficacy analyses will be based on the Efficacy Population.

The primary efficacy endpoint will be the change from baseline in htTKV at Month 12. An analysis of covariance model including treatment group as a factor and the baseline htTKV as a covariate will be used for efficacy analyses. The Type I error rate will be set at an alpha level of 0.05. Additional efficacy endpoints include change from baseline in htTKV at Months 18, 24, and 30 days post-dose.

In addition, the change in eGFR at the Month 12, 18, 24, and 30-days post-treatment time points will be evaluated.

9.11. Safety Analyses

Safety analyses will be based on the mITT Population.

Treatment-emergent adverse events (TEAE) will be coded using the Medical Dictionary for Regulatory Activities (Version 19.0 or higher). The number of events, incidence, and percentage of TEAEs will be presented by system organ class and by preferred term for each treatment group. Treatment-emergent adverse events will be further summarized by severity and relationship to investigational product. Adverse events related to investigational product, AEs leading to withdrawal, SAEs, and deaths will be summarized/listed.

Clinical laboratory tests (including serum creatinine, cystatin C, and eGFR), vital signs, and ECG findings will be summarized by treatment group and visit. Potentially clinically important findings will also be summarized or listed.

Physical examination, echocardiogram and ocular evaluation findings will be provided in listings.

9.12. Sample Size Calculation and Power Considerations

Based on the results presented in Caroli, et.al. it is anticipated that the mean change from baseline in htTKV at 12 months will be $83.6 (\pm 90.0)$ mL in the placebo group. Assuming the mean change from baseline in htTKV at 12 months is 26.4 mL for the tesevatinib group, 40 subjects per group would yield approximately 80% power to detect a difference between treatment groups based on a 2-sided t-test with a Type I error rate of 0.05. Ten additional subjects per group will be added (ie, for a total of 50 subjects per group) to adjust for dropouts and differences in analysis methodologies (eg, the htTKV data will be log-transformed).

